6.1 EXPLORATORY ENDPOINTS

Non-invasive methods for monitoring health-related biomarkers in liquids such as plasma ("liquid biopsy") have already been successfully introduced in a wide range of contexts. cfDNA is extremely dynamic and responsive, providing strong indicators of immune response or infection, also revealing the cells of origin undergoing apoptosis or necrosis. We will profile cfDNA isolated from plasma samples before, during, and after influenza therapy to evaluate the utility of cfDNA as a means to monitor damage caused by viral infection as response to therapy. cfDNA analysis will be performed by our collaborator [name]

5.2 METHOD OF ANALYSIS

Plasma from patients of each arm was centrifuged at 16,000 g for 10 minutes. cfDNA extraction will be performed according to manufacturer recommendations (QIAGEN MinElute Circulating Nucleic Acid Kit, reference #55204 or QIAGEN EZ1 Virus Mini Kit v2.0 955134) at 0.4-1 mL plasma input. DNA sequencing of bisulfite-treated cfDNA will be used to reveal methylation patterns with single nucleotide resolution. Because these patterns are cell, tissue, and organ types specific, they can inform the origins of cfDNA. Levels of cfDNA and tissue of origins will be compared for patients in each arm before during and after therapy as described(Bezdan, Grigorev et al. 2020)

6. INVESTIGATOR REQUIREMENTS

7.1 RETENTION OF RECORDS

FDA regulations (21 CFR §312.62[c]) and the ICH Guideline for GCP (see Section 4.9 of the guideline) require that records and documents pertaining to the conduct of clinical trials and the distribution of investigational drug, patient records, consent forms, laboratory test results, and medication inventory records, must be retained for 2 years after the last marketing application approval in an ICH region or after at least 2 years have elapsed since formal discontinuation of clinical development of the investigational product. All state and local laws for retention of records also apply.

For studies conducted outside the U.S. under a U.S. IND, the Principal Investigator must comply with the record retention requirements set forth in the FDA IND regulations and the relevant national and local health authorities, whichever is longer.

6.2 STUDY MEDICAL MONITORING REQUIREMENTS

This clinical research study will be monitored both internally by the PI and externally by the Weill Cornell Medicine IRB. In terms of internal review, the PI will continuously monitor and tabulate AEs. Appropriate reporting to the Weill Cornell Medicine IRB will be made. The PI of this study will also continuously monitor the conduct, data, and safety of this study to ensure that:

- Interim analyses occur as scheduled,
- Stopping rules for toxicity and/or response are met,
- Risk/benefit ratio is not altered to the detriment of the subjects,
- Appropriate internal monitoring of AEs and outcomes is done,
- Over-accrual does not occur,
- Under-accrual is addressed with appropriate amendments or actions, and
- Data are being appropriately collected in a reasonably timely manner.

Routine monitoring will be carried out via a periodic team conference among investigators during which toxicity data, including all SAEs, will be reviewed and other issues relevant to the study such as interim assessment of accrual, outcome, and compliance with study guidelines, will be discussed. Monitoring will be carried out on an ongoing basis. The severity, relatedness, and whether or not the event is expected will be reviewed.

6.3 STUDY MEDICATION ACCOUNTABILITY

The Sponsor Investigator of the study will ensure maintenance of complete and accurate records of the receipt, dispensation, and disposal or return of all study drug in accordance with 21 Code of Federal Regulations (CFR), Part 312.57 and 312.62 and Genentech requirements.

All unused remaining product at the end of the study should be disposed of at the study site according to institutional standard operating procedure. If there is no SOP at the site for drug destruction, return study drug with the Inventory of Returned Clinical Material form as directed by Genentech.

6.4 DATA COLLECTION

The study coordinator and investigators are responsible for ensuring that the eligibility checklist is completed in a legible and timely manner for every patient enrolled in the study, and that data are recorded on the appropriate forms and in a timely manner. Any errors on source data should be lined through, but not obliterated, with the correction inserted, initialed, and dated by the study coordinator or PI. All source documents will be available for inspection by the FDA and the Weill Cornell Medicine IRB.

7.2 INFORMED CONSENT

The informed consent document must be signed by the subject or the subject's legally authorized representative before his or her participation in the study. The case history for each subject shall document that informed consent was obtained prior to participation in the study. A copy of the informed consent document must be provided to the subject or the subject's legally authorized representative. If applicable, it will be provided in a certified translation of the local language.

Signed consent forms must remain in each subject's study file and must be available for verification by study monitors at any time.

7.3 INSTITUTIONAL REVIEW BOARD OR ETHICS COMMITTEE

This protocol, the informed consent document, and relevant supporting information must be submitted to the IRB for review and must be approved before the study is initiated. The study will be conducted in accordance with FDA, applicable national and local health authorities, and IRB requirements. The Principal Investigator is responsible for keeping the IRB apprised of the progress of the study and of any changes made to the protocol as deemed appropriate, but in any case, the IRB must be updated at least once a year. The Principal Investigator must also keep the IRB informed of any significant AEs.

Investigators are required to promptly notify their respective IRB of all adverse drug reactions that are both serious and unexpected. This generally refers to SAEs that are not already identified in the Investigator's Brochure and that are considered possibly or probably related to the molecule or study drug by the investigator. Some IRBs may have other specific AE requirements to which investigators are expected to adhere. Investigators must immediately forward to their IRB any written safety report or update provided by Genentech (e.g., IND safety report, Investigator's Brochure, safety amendments and updates, etc.).

7.4 CONFIDENTIALITY

Patient medical information obtained by this study is confidential and may be disclosed to third parties only as permitted by the ICF (or separate authorization to use and disclose personal health information) signed by the patient or unless permitted or required by law.

Medical information may be given to a patient's personal physician or other appropriate medical personnel responsible for the patient's welfare for treatment purposes.

Data generated by this study must be available for inspection upon request by representatives of the FDA and other regulatory agencies, national and local health authorities, Genentech representatives and collaborators, and the IRB/Ethics Committee (EC) for each study site, if appropriate.

Appendix 1 - Study Flowchart

Day(s)	D1	D2^a	D3	D4	D5	D6	D7	D8	D9	D10	D11 – D14	D15^b	EOS D30^{b,c}	Unsched Visit
On-site study visit	x	(x)		x			x			x		x	x	
Phone Visit			x	x		x	x		x	x				
Screening	x													
Informed consent and assent	x													
Inclusion/Exclusion criteria	x													
Randomization^d	x													
Demographics	x													
Medical history	x													
Concomitant medication monitoring	x			x			x			x		x	x	x
Physical examination^e	x ^e	x		x			x			x		x ^f	x ^f	x ^g
Body weight	x											x ^f		
Vital sign measurements^h	x											x ^f	x ^f	x ^g
Presence or absence of respiratory supportⁱ	x	x		x			x			x		x ^f	x ^f	x ^g
Blood hematology and chemistry^j	x			x ^f			x			x		x ^f	x ^f	x ^g
Blood liver chemistry^k	x			x			x			x		x ^f	x ^f	
Blood for exploratory biomarkers	x	x		x			x			x		x	x	
NP swab^l	x	x		x			x			x		x	x	x ^a
Chest X-ray/CT Scan^m	x													

Day(s)	D1	D2 ^a	D3	D4	D5	D6	D7	D8	D9	D10	D11 – D14	D15 ^b	EOS D30 ^{b,c}	Unsched Visit
On-site study visit	x	(x)		x			x			x		x	x	
Phone Visit		x	x		x	x		x	x					
Pregnancy test ⁿ	x													
Adverse events		x		x			x			x		x	x	x
Patient self assessment ^o	x	x	x	x	x	x	x	x	x	x	x	x	x	x
Xofluza/Placebo ^p	x			x			x							
NAI SOC (Oseltamivir) ^q	x	x	x	x	x	x	x	x	x	x				

CT = computed tomography; D = day; EOS = end of study; Hosp = Hospitalized; NAI = neuraminidase inhibitor; Random = Randomization; RIDT = Rapid Influenza Diagnostic Test; RT-PCR = reverse transcription polymerase chain reaction; SOC = standard-of-care; Unsched = Unscheduled; V = visit; VHP = Voluntary Harmonization Procedure.

- a. Optional visit
- b. A visit window of ± 2 days applicable.
- c. The EOS visit should occur approximately 20 days after the last dose of study drug.
- d. Randomization should occur as soon as possible, after screening and informed consent.
- e. A complete physical examination should be conducted at screening. At post baseline visits and as clinically indicated, limited, symptom directed physical examinations should be performed.
- f. Clinical procedures may be undertaken at investigator's discretion if symptoms and signs persist beyond the treatment period or if viral shedding is detected beyond Day 10.
- g. Perform assessments at any unscheduled visits based upon clinician's discretion.
- h. During the study treatment period (Day 1/Visit 1 to Day 10), all vital sign measurements (i.e., respiratory rate, pulse rate, peripheral oxygen saturation, systolic and diastolic blood pressures, and body temperature) should be recorded when on-site. For all other visits, the only vital signs measurement taken will be temperature. After day 10 vital sign measurements and specific assessments are to be recorded at the investigators' discretion (e.g., if symptoms and signs persist during follow-up).
- i. Presence or absence and type of respiratory support; oxygen saturation.
- j. See Section X for tests included in laboratory panels.

- k. Liver function test results to be reviewed by the investigator before Xofluza, or its matching placebo, is administered. On Day 1, prior blood results if tests conducted within 24 hours prior to screening. On Day 4 and day 7, blood liver chemistry panel should be reviewed before the patient will receive Xofluza or matching placebo on this study day.
 - l. Nasopharyngeal swabs for RT-PCR: RT-PCR for influenza and covid-19 should be performed at screening.
 - m. If a chest X-ray has not been taken within the 24 hours prior to screening, it will be performed per clinical provider decision. If the SOC is a chest CT scan, this can be used as alternative to the chest X-ray per clinical provider decision.
 - n. All women of childbearing potential will have a pregnancy test at screening (urine or serum).
 - o. Self-assessment of seven influenza-associated symptoms (cough, sore throat, headache, nasal congestion, feverishness or chills, muscle or joint pain, and fatigue) on a four-point scale (with 0 indicating no symptoms, 1 mild symptoms, 2 moderate symptoms, and 3 severe symptoms) twice daily from enrolment (day 1) until day 9 and once daily on days 10–15, and record their results in the patient diary.
 - p. Baloxavir treatment or Baloxavir-matched placebo dosing will occur on Day 1 and Day 4, with a further dose at Day 7
 - q. The SOC NAI (Oseltamivir) will be administered from Day 1 through Day 10.

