10. Safety and tolerability of Baloxavir in Combination with SOC treatment as assessed by Percentage of Participants with Adverse Events (AEs) [Time Frame: From first dose of study drug to Day 15]

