Oral temperature will be measured by the patient (in the outpatient setting) or by the staff for inpatients in the am and pm daily until day 10.

To evaluate **incidence of complications associated with influenza** after the start of study treatment, at each study visit investigators will assess whether each of the complications (sinusitis, otitis, bronchitis, pneumonia) is present or not. If present, the report form shown in section will be completed. For pneumonia, a radiological confirmation will be required.

On days 1, 7 and 15 safety laboratory tests (CBC, blood chemistry with LFTs) will be done.

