4.5 STUDY ASSESSMENTS

The schedule of activities to be performed during the study is provided in Appendix 1. All activities must be performed and documented for each patient. Patients will be closely monitored for safety and tolerability throughout the study. Patients should be assessed for toxicity prior to each dose; dosing will occur only if the clinical assessment and local laboratory test values are acceptable.

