5.3.2 ADVERSE EVENT REPORTING PERIOD

The study period during which AEs and SAEs as described in **section J** where the patient has been exposed to Genentech product must be reported. Reporting period begins after informed consent is obtained and initiation of study treatment and ends 30 days following the first administration of study treatment or study discontinuation/termination, whichever is earlier. After this period, investigators should only report SAEs that are attributed to prior study treatment.

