5.3.3 ASSESSMENT OF ADVERSE EVENTS

All AEs and SAEs whether volunteered by the subject, discovered by study personnel during questioning, or detected through physical examination, laboratory test, or other means will be reported appropriately. Each reported AE or SAE will be described by its duration (i.e., start and end dates), regulatory seriousness criteria if applicable, suspected relationship to the baloxavir combination therapy (see following guidance), and actions taken.

To ensure consistency of AE and SAE causality assessments, investigators should apply the following general guideline:

YES

There is a plausible temporal relationship between the onset of the AE and administration of the baloxavir combination therapy and the AE cannot be readily explained by the subject's clinical state, intercurrent illness, or concomitant therapies; and/or the AE follows a known pattern of response to the baloxavir combination therapy or with similar treatments; and/or the AE abates or resolves upon discontinuation of the baloxavir combination therapy or dose reduction and, if applicable, reappears upon re- challenge.

NO

Evidence exists that the AE has an etiology other than the baloxavir combination therapy (e.g., preexisting medical condition, underlying disease, intercurrent illness, or concomitant medication); and/or the AE has no plausible temporal relationship to baloxavir combination therapy administration (e.g., cancer diagnosed 2 days after first dose of study drug).

Expected adverse events are those adverse events that are listed or characterized in the Package Insert (P.I) or current Investigator Brochure (I.B).

Unexpected adverse events are those not listed in the P.I or current I.B or not identified. This includes adverse events for which the specificity or severity is not consistent with the description in the P.I. or I.B. For example, under this definition, hepatic necrosis would be unexpected if the P.I. or I.B. only referred to elevated hepatic enzymes or hepatitis.

For patients receiving combination therapy, causality will be assessed individually for each protocol-mandated therapy.

5.3.4 Management Criteria for Abnormal Liver Function Tests and Data and Safety Monitoring Plan (DSMP)

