For secondary viral loads related endpoints, summary statistics in terms of mean, standard deviation, median and range will be calculated for each arm at each time points among patients with relevant measurements. Longitudinal analyses using mixed effects repeated measures will be used to model the mean viral loads overall time. Contrasts of interest including between arm differences will be explored using simultaneous tests of general linear hypotheses. If normality is a concern, log-transformed and standardized viral load data will be used. Longitudinal analysis will be carried out among patients with at least one relevant viral load measurement. Kaplan-Meier estimates will be generated for time to events endpoints such as time to Improvement of Individual Influenza Symptoms, the time to viral clearance and time to return to preinfluenza health status for each study arm. Between study arm difference in these endpoints will be explored using the generalized Wilcoxon test.

Categorical data such as the occurrence of treatment-emergent variants of neuraminidase and polymerase by direct next-generation sequencing and AE's will be summarized in terms of counts and proportions separately for each arm.

Between arm difference in the categorical variable will be explored using Fisher's exact test. The study is likely will not have adequate power to detect between arm differences and all the between arms comparisons are considered exploratory. Summary statistics generated for study endpoints for each arm will provide useful information for planning future studies.

The power calculations were performed using PASS 15 Power Analysis and Sample Size Software (2017). NCSS, LLC. Kaysville, Utah, USA, ncss.com/software/pass. All comparisons will be two-tailed, with a significance level at 0.05 and 95% confidence intervals will also be reported. All analyses will be performed in SAS Version 9.4 (2019), SAS Institute, Inc., Cary, NC; and R Version 4.0.4 (2021).

Note: The statistical considerations section was written by [name], MS, and revised by [name], in the Division of Biostatistics, Department of Population Health Sciences, Weill Cornell Medicine.

Influenza sequence analysis will be performed by [name], Director of Systems Genomics Section at the Laboratory of Parasitic Diseases of NIAID/NIH and expert in Influenza evolution.

No interim analysis is planned for this study

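### The flowchart lets safety testing after Day 10 depend on persistent illness or shedding, contradicts Section 3.1 on the Day 15 laboratory tests, and could under-count test-detected adverse events in the faster-clearing arm

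*Combined protocol and SAP*

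**What the plan says.** In Appendix 1, note f is attached at Day 15 and Day 30 to five rows: physical examination, vital signs, respiratory support, hematology and chemistry, and liver chemistry. These may be "undertaken at investigator's discretion if symptoms and signs persist beyond the treatment period or if viral shedding is detected beyond Day 10". Note h adds: "After day 10 vital sign measurements and specific assessments are to be recorded at the investigators' discretion". Other rows at the same visits, including adverse events and blood for biomarkers, carry a plain mark with no condition. Note f is also printed on Day 4 hematology and chemistry.

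The body text differs. Section 3.1 states: "On days 1, 7 and 15 safety laboratory tests (CBC, blood chemistry with LFTs) will be done". Section 4.5, which introduces the flowchart, states: "All activities must be performed and documented for each patient".

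On counting events, Section 5.3.3 says that adverse events "detected through physical examination, laboratory test, or other means will be reported appropriately". Secondary endpoint 10 in Section 2.1, the percentage of participants with adverse events, has "Time Frame: From first dose of study drug to Day 15". The reporting period in Section 5.3.2 "ends 30 days following the first administration of study treatment or study discontinuation/termination, whichever is earlier". The Statistical Considerations section summarises adverse events by arm as categorical data and adds: "Between arm difference in the categorical variable will be explored using Fisher's exact test".

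**The concern.** Symptom duration and viral clearance are efficacy outcomes here. If they decide who is examined or has blood taken after Day 10, the search for harms depends on a post-randomisation outcome that treatment may change. An asymptomatic rise in liver enzymes or a fall in a blood count is found only in a patient who is tested. An arm whose patients recover sooner would be tested less and could appear safer for that reason alone. Randomisation does not prevent this, because the trigger arises after it. Blinding does not prevent it either, because the investigator responds to the patient's illness and does not need to know the treatment.

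What is at stake is the adverse-event summary by arm, which the Statistical Considerations section intends to be useful in planning later studies. The last baloxavir or placebo dose is on Day 7, so the days after Day 10 are relevant to safety.

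**Working it through.** The plan states no figure on this point, so there is none to reproduce. The check has two parts.

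**1. Which post-Day-10 ascertainment is conditional**

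- *Day 15 laboratory tests:* unconditional in Section 3.1, conditional in Appendix 1 note f. This is a contradiction.
- *Day 15 examination, vital signs and respiratory check:* conditional (notes f and h). Section 3.1 does not cover them.
- *Day 30 examination, vital signs, respiratory check and laboratory tests:* conditional. These lie outside the endpoint 10 window but inside the 30-day reporting period.
- *Adverse-event questioning:* unconditional at both visits (Appendix 1; Section 5.4.1 asks for a consistent method throughout).
- *Complication enquiry* (each visit, Sections 3.1 and 4.5.6) and *hospital recovery scale* (Day 1 to Day 30, Section 4.5.6): unconditional.

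Days 11 to 15 are 5/15 = 33% of the endpoint 10 window. Days 11 to 30 are 20/30 = 67% of the reporting period.

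**2. How large the effect could be**

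Let p0 be the proportion with an adverse event by Day 10, q the rate after Day 10 of events that only a test or examination would find, and s the share of an arm still tested. Untested patients are assumed never to be detected, which is a worst case. True rates are equal in the two arms.

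Observed proportion = p0 + (1 − p0) × q × s

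Spurious difference = (1 − p0) × q × (s_control − s_baloxavir)

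Inputs: p0 is set at 0.45 to 0.50, guided by the 45.2% and 50.0% in the adverse-event table of Section 1.3, which come from another study. The values q = 0.10 to 0.30 and all the shares s are assumptions with no source in the documents.

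| Share tested, control vs baloxavir | Spurious difference, points | Patients per 15 | Fisher rejection rate |
|---|---|---|---|
| 40% vs 20% | 1.0 to 3.3 | 0.15 to 0.50 | 1.7% to 1.8% |
| 60% vs 30% | 1.5 to 5.0 | 0.23 to 0.74 | 1.7% to 2.0% |
| 80% vs 20% | 3.0 to 9.9 | 0.45 to 1.49 | 1.8% to 3.3% |

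Smallest case: 0.50 × 0.10 × 0.20 = 0.010. Largest case: 0.55 × 0.30 × 0.60 = 0.099. With no ascertainment difference, Fisher's test at 15 vs 15 rejects in 1.6% to 1.7% of trials, so even the largest case stays below 5%.

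Precision for comparison: the 95% half-width for a difference near 50% is 1.96 × √(2 × 0.25/15) = 0.358, about 36 points.

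Among late test-detected events alone, the observed ratio under equal true rates is s_baloxavir/s_control: 0.5 in the first two rows and 0.25 in the third. That ratio does not depend on q or on sample size.

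If the arms clear equally, the shares are equal and the difference is 0. If baloxavir clears more slowly, the sign reverses.

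**The case against.** The strongest reply is that Section 3.1 already requires the Day 15 laboratory tests and Section 4.5 requires all activities for each patient. As endpoint 10 stops at Day 15, its laboratory component is then complete. This stands if Section 3.1 governs, but the documents do not say that it does. The activities named in Section 4.5 are those of Appendix 1, which contains note f.

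Other limits also stand. Note f is permissive and triggers nothing automatically. Section 4.2.1 freezes swabs for assay at the end of the clinical period, so it is unclear how shedding beyond Day 10 would be known in time, although Section 3.1 assumes that it is. The symptom condition can work from the diary. Post-baseline examinations are limited and symptom-directed at every visit (Section 4.5.3 and note e), so examination findings depend on symptoms before Day 10 as well. All between-arm comparisons are declared exploratory.

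A reader might infer that the adverse-event comparison is biased towards baloxavir. The documents do not support that as a fact, because faster clearance on the combination is the hypothesis under test. A reader might also infer that a comparison of events of special interest is distorted. The Statistical Considerations section names no such comparison; Section 5.4.4 defines these events for rapid communication.

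**Conclusion.** The concern holds in a limited form. Appendix 1 permits outcome-dependent safety testing after Day 10 and contradicts Section 3.1 on the Day 15 laboratory tests. If the flowchart is followed, events detected by test or examination could be under-counted in the faster-clearing arm, and the planned analysis would not show it. Events elicited by questioning are not affected.

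The size, about 1 to 10 points on any adverse event, rests on assumed testing shares and late event rates and on no detection at all in untested patients. It is small beside a half-width of about 36 points and does not push Fisher's test above its nominal level. The reason to act is that the distortion follows efficacy, would not shrink in a larger trial, and is cheap to remove.

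Cutting the whole comparison at Day 10 might look like the natural remedy, but it does not work. Day 4 hematology also carries note f, examinations are symptom-directed throughout, and the cut would discard the Day 15 laboratory results that Section 3.1 requires.

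**What to change.** 1. Reconcile notes f and h, including the note f printed on Day 4 hematology, with Section 3.1. The Day 15 safety laboratory tests used for endpoint 10 should be protocol-scheduled for every patient, regardless of symptoms or shedding. Clinician-directed testing stays at the investigator's discretion.

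2. In the Statistical Considerations section, base the between-arm comparison of laboratory-detected adverse events on scheduled laboratory visits common to all patients, through Day 15 once reconciled. Flag findings from outcome-triggered assessments, including the Day 30 tests, and list them by arm with the number tested and no between-arm test. Keep elicited adverse events and serious adverse events in the full-window comparison.

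Cost: a few more routine local laboratory results at Day 15, an on-site visit where Appendix 1 already has blood drawn for biomarkers; one flag in the adverse-event data; and a few sentences of text. No sample-size or power figure changes. With equal testing in both arms, the spurious difference in the illustration becomes 0.
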